7.1.3.6 Osteogenesis Imperfecta specific Quality of Life Questionnaire for Adults (OIQoL-A)

OIQoL-A

The OIQoL-A is a PRO instrument for use in adults with OI Type I, III, or IV. The OIQoL-A currently measures 5 areas of quality of life related to OI (Physical Function, Pain, Hearing Loss, taking care/Concerns, Social and Family Life and Activities). For each visit the OIQoL-A total score and pain and activity subscale scores will be derived. Please see Appendix C for detailed scoring of the total and subscale scores.

7.1.4 Definitions relative to safety parameters

7.1.4.1 Adverse Event (AE)

Treatment Emergent Adverse Event (TEAE)

A Treatment Emergent AE (TEAE) is defined as an AE occurring or worsening on or after the first dose of study medication. AEs that occurred for subjects while taking placebo prior to protocol amendment 4.0 will not be considered treatment emergent for the active treatment groups. TEAEs will also be split between AEs that started during the Patient's treatment period and those that start on or after the first day of the follow-up period.

Duration of AEs

The duration of an AE will be calculated as the resolution date minus the start date plus 1.

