7.4. Screen Failures

Screen failures are defined as participants who consent to participate in the clinical study but are not subsequently randomised. A minimal set of screen failure information is required to ensure transparent reporting of screen failure participants to meet the Consolidated Standards of Reporting Trials (CONSORT) publishing requirements and to respond to queries from regulatory authorities. Minimal information includes demography, screen failure details, eligibility criteria, and any serious adverse events (SAE) and adverse events of special interest (AESI).

Individuals who do not meet the criteria for participation in this study (screen failure) may not be rescreened.

However, the screening period may be extended beyond 28 days in the following circumstances with the discussion and with the approval of the medical monitor:

- All screening inclusion/exclusion criteria are met but the participant's schedule, including genetic testing or HRpQCT scan, prevented them from being randomised within the screening period.

Additionally, individual lab parameters or screening test may be repeated if the result is considered aberrant or not clinically consistent with the patient's health status. Decisions to re-test should be made in conjunction with the study medical monitor.

Participants who have individual laboratory parameters re-tested should have the results entered in the electronic case report form (eCRF).

8. Treatments

Study treatment is defined as any investigational treatment(s), marketed product(s), placebo, or medical device(s) intended to be administered to a study participant according to the study protocol.

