11.3.2. Safety Analyses

All safety analyses will be performed on the Safety Population.

Endpoint	Statistical Analysis Methods
Primary	
Adverse Events
 
AEs will be coded using the most recent version available of the Medical Dictionary for Regulatory Activities (MedDRA). Summaries will be by system organ class and preferred term. TEAEs are defined as any AE occurring or worsening on or after the first dose of study medication. If a participant experiences the same preferred term multiple times then the event will be counted only once and by the greatest severity.
 
The frequency and incidence of TEAEs will be presented by system organ class and preferred term for each treatment regimen (number and percentage of participants experiencing at least 1 AE per preferred term as well as the number of observed events per preferred term). These tables will be presented on both the pooled and the non-pooled version of the Safety population.
 
Remaining safety tables will be on the pooled version of the Safety population only.
 
Separate tables will be presented by severity and by relationship. All AEs will be presented in full in a comprehensive listing including participant number, treatment regimen, severity, seriousness, action taken, outcome, relationship to treatment, onset/stop and duration. Details of SAEs/AESIs and AEs leading to withdrawal will be listed separately.

Secondary	
All secondary safety analyses will be on the pooled version of the Safety population only.
 
Infusion Site reactions
 
Infusion site reactions will be tabulated and summarised by treatment regimen.

Endpoint	Statistical Analysis Methods

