3 STUDY DESIGN

3.1 General study design

MBPS205 is a phase 2, multicentre, multinational, double-blind, dose range-finding study comparing 3 blinded doses of setrusumab (20 mg/kg, 8 mg/kg and 2 mg/kg) and an open-label treatment arm (20 mg/kg).

[figure not shown]
Following a screening period lasting up to 28 days, eligible participants will be randomised 1:1:1:1 into the 4 treatment arms stratified by OI type (Type I or III/IV) and will receive study treatment (setrusumab) for 12 months. Any participants assigned to placebo according to the previous MBPS205 protocol design will be transferred to open-label 20 mg/kg treatment for 12 months.

Participants will have HRpQCT scans of their non-dominant distal radius at baseline, 3-month (for open-label participants only), 6-month and 12-month time points to determine the effect of treatment on Tr. vBMD. The primary analysis will be conducted once all data up to month 12 has been collected for the blinded treatment groups.

Following completion of the study treatment participants can receive an optional single dose of zoledronic acid and will enter 12 months follow-up period and will have visits at Months 14, 18 and 24 to establish the rate of offset of treatment effect. Participants will also receive follow-up telephone calls at Months 16 and 21. Participants can receive an optional further dose of zoledronic acid at Month 18 at the discretion of their treating physician. During the follow-up period participants will have HRpQCT scans of their non-dominant distal radius and tibia at Month 18 and Month 24.

The Study Flow Chart is presented in Figure 1.

Figure 1: Study Flow Chart

An Independent Data Monitoring Committee will monitor safety throughout the study and make recommendations on the selected dose.

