6 ANALYSIS POPULATIONS

Analyses for the primary efficacy endpoints and selected secondary endpoints will be analysed on the FAS, the Non-restricted FAS and the PP samples, while analyses for the remaining secondary efficacy endpoints will be analysed on the FAS sample only. Data collected for patients while taking placebo prior to protocol amendment 4.0 will not be included in any efficacy analysis (i.e. treatment comparisons), however will be included in efficacy descriptive statistic summaries.

Safety and tolerability endpoints will be analysed using the safety population. Data collected for patients while taking placebo prior to protocol amendment 4.0 will be included in all safety summaries.

Pharmacokinetic data will be analysed using the PK population.

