7 STATISTICAL CONSIDERATIONS AND ANALYSIS

7.1 Derived Variables

7.1.1 General Variables

Study Day

The derived study day will be relative to the date of first active (i.e non-placebo) study medication (Derived Study Day 1) and calculated as:

- (assessment date – date of first dose of study medication) + 1, for assessments on or after the first dose of study medication
- (assessment date – date of first dose of study medication), for assessments prior to date of first dose of study medication.

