7.1.4.3 Prior, Concomitant and Follow-up Medications/Procedures

Medications and Procedures will be assigned as being prior to study treatment, concomitant with study treatment or taken during the follow-up phase based on the start and stop dates of the medication and dosing dates.

If the medication/procedure stop date is before the date of the first dose of study medication, the medication/procedure will be assigned as being prior to study treatment. Otherwise, the medication/procedure will be assigned as being concomitant with study treatment unless the start date of the medication/procedure is after the date of entry into the follow-up period, when it will then be classified as occurring in the follow-up phase.

Medications/procedures that occurred for patients while taking placebo (prior to protocol amendment 4.0) will be considered as being prior to study medication as well as concomitant for placebo.

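### SAP 7.1.4.1, read literally, keeps adverse events that occurred on placebo out of the active-group TEAE tables with no exception for worsening after the switch to open-label 20 mg/kg, which conflicts with the TEAE definition

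*SAP*

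**What the plan says.** **Definition.** SAP 7.1.4.1 says a TEAE "is defined as an AE occurring or worsening on or after the first dose of study medication". Protocol 11.3.2 agrees: "TEAEs are defined as any AE occurring or worsening on or after the first dose of study medication".

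**Placebo sentence.** SAP 7.1.4.1 continues: "AEs that occurred for subjects while taking placebo prior to protocol amendment 4.0 will not be considered treatment emergent for the active treatment groups". Worsening after the switch is not mentioned.

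**Who is affected.** Under SAP 3.1, participants assigned to placebo in the previous design "will be transferred to open-label 20 mg/kg treatment for 12 months". Neither document says how many there were.

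**Where placebo data go.** SAP Section 6 says: "Data collected for patients while taking placebo prior to protocol amendment 4.0 will be included in all safety summaries". SAP 8.1.2 lists placebo as a displayed group.

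**Which first dose.** SAP 7.1.1 ties study day to active drug: "The derived study day will be relative to the date of first active (i.e non-placebo) study medication". The TEAE definition has no such tie, and the opening of Protocol Section 8 counts placebo as study treatment.

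**Medications and procedures.** The general rule in SAP 7.1.4.3 makes anything not stopped before first dose concomitant, unless it starts after entry into follow-up. Those that occurred during placebo "will be considered as being prior to study medication as well as concomitant for placebo".

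**The concern.** For a participant who switches, time on placebo is the pre-treatment period for setrusumab. An event present at the switch that gets worse on active drug is the case the worsening clause exists to catch. The placebo sentence, taken as written, takes that case out again.

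The TEAE flag drives the tables by system organ class and preferred term, by maximum severity and by relationship (SAP 8.6.1), and the AESI table (SAP 8.6.1.1). The people concerned receive the highest dose studied. Elsewhere the SAP resolves doubt conservatively: an unclear onset date counts as treatment-emergent (7.2.2.4), and missing intensity and causality count as severe and related (8.6.1). This rule works in the opposite direction, and SAP Section 9 declares no change from the protocol.

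The medication rule raises a separate, smaller question. A drug begun on placebo and continued through setrusumab treatment might not appear as concomitant for open-label 20 mg/kg. That would weaken the table a reader would use to look for confounding, including by the classes that Protocol 8.6 does not permit.

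**Working it through.** The documents state no figure that could be reproduced, so the check compares the rules.

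**Step 1. Four kinds of event under two meanings of first dose.** The table shows whether the event counts as treatment-emergent in the active column.

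| Event in a switched participant | General definition, first dose = first active dose | General definition, first dose = first placebo dose | After the placebo sentence, read literally |
|---|---|---|---|
| 1. Starts and ends on placebo | No | Yes | No |
| 2. Starts on placebo, continues unchanged | No | Yes | No |
| 3. Starts on placebo, worsens on setrusumab | Yes | Yes | No |
| 4. Starts on setrusumab | Yes | Yes | Yes |

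- If first dose is the first active dose, the sentence changes row 3 only. Rows 1 and 2 were already out and row 4 is untouched. The SAP leans towards this meaning: study day uses this anchor (7.1.1), and assessments made on placebo may serve as baseline (8.1.5).
- If first dose is the first placebo dose, the sentence does useful work in rows 1 and 2, because it keeps placebo-period events out of the active columns. It still excludes row 3, and no other text moves a worsened event to open-label 20 mg/kg. At most the event appears under placebo.

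Row 3 therefore gives the same conflict with the definition on either meaning.

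**Step 2. Does data recording resolve row 3?** Protocol Appendix 4 lists exacerbation of a pre-existing condition as meeting the AE definition. If the worsening is entered as a new AE with onset on setrusumab, row 3 becomes row 4 and is counted. No text requires a new record, and the follow-up provisions in Appendix 4 also allow an existing report to be updated. The exposed events are thus row 3 events not entered as new records.

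**Step 3. Size.** Let k be the number of participants missing from a table row because their only qualifying event for that row is such an event. Then

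loss in the incidence shown = k / n.

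Neither the number who switched nor the frequency of worsening is given, so k cannot be derived and may be 0. Assuming n equals the planned open-label arm of 25 (SAP Section 5):

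- k = 1: 1/25 = 4 percentage points
- k = 2: 2/25 = 8 percentage points
- k = 3: 3/25 = 12 percentage points

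These figures show only what each missed participant is worth.

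**Step 4. Medications.** By the general rule, a drug begun on placebo and not stopped before the first active dose would be concomitant with setrusumab. The placebo sentence gives it two labels, prior and concomitant for placebo, and does not say whether the third applies. No AE table uses this label.

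**The case against.** The strongest reply is that the placebo sentence is only an attribution rule. Because the protocol counts placebo as study treatment, something must keep placebo-period events out of the setrusumab columns, and a worsening after the switch happens on setrusumab. That purpose is sensible, and it is right for events that do not worsen. But the sentence gives no exception for those that do, and a programmer following it would exclude them.

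Several further points stand and limit the concern:

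- A reader might infer that every worsened event is lost. The documents do not support that: the SAP is silent on worsening, and an exacerbation may be recorded as a new AE.
- A new fracture or cardiovascular event after the switch is a new occurrence, so the AESI table is exposed only through an event that began on placebo and worsened.
- The events do not vanish from the report. The overall AE summary is not confined to TEAEs, all AEs are listed in full (SAP 8.6.1), and safety data are not tested statistically (SAP 8.6).
- Medication labels enter no AE count, so that part cannot make setrusumab look safer. The two labels in SAP 7.1.4.3 are not exclusive, so a third is not ruled out.
- It would be wrong to say that a blinded within-person comparison is lost. Treatment after the switch is open-label, and the SAP's AE sections plan no such comparison.

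**Conclusion.** The point holds as a conflict between the literal rule and the plan's own definition. SAP 7.1.4.1 contains no route by which an AE that began on placebo and worsened on open-label 20 mg/kg is counted as treatment-emergent for that arm, although the preceding sentence and Protocol 11.3.2 would count it. Such events, if not entered as new records, could be missing from the open-label TEAE, severity and AESI tables.

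Any omission would lower the active-arm counts, but its size is unknown. The figure of 4 percentage points per participant assumes a denominator of 25 and that the participant has no other qualifying event in the same row. A reader might go further and conclude that the safety of 20 mg/kg is understated. The documents show that this is possible, not that it happens.

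The medication rule is a separate gap, confined to the concomitant medication and procedure tables.

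**What to change.** **SAP 7.1.4.1.** State that, for participants who switched from placebo, first dose means the first active dose. Add that an AE with onset on placebo which worsens in severity or becomes serious on or after that dose is treatment-emergent for open-label 20 mg/kg. Placebo-period events that do not worsen stay out of the active columns, as now.

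**SAP 7.1.4.3.** State that medications or procedures ongoing at the first active dose are also concomitant for open-label 20 mg/kg, in addition to the two labels they already carry.

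**Cost.** A few sentences and minor programming. The team should also confirm how worsening is captured in the eCRF, because the rule needs the change and its date, or a new record. Open-label TEAE counts may rise slightly.

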7.1.4.2 Treatment Compliance

Duration of Exposure

The duration of Exposure to study medication (number of days) will be defined as:

(date of last dose of study medication – date of first dose of study medication) + 28 days

7.1.4.3 Prior, Concomitant and Follow-up Medications/Procedures

Medications and Procedures will be assigned as being prior to study treatment, concomitant with study treatment or taken during the follow-up phase based on the start and stop dates of the medication and dosing dates.

If the medication/procedure stop date is before the date of the first dose of study medication, the medication/procedure will be assigned as being prior to study treatment. Otherwise, the medication/procedure will be assigned as being concomitant with study treatment unless the start date of the medication/procedure is after the date of entry into the follow-up period, when it will then be classified as occurring in the follow-up phase.

Medications/procedures that occurred for patients while taking placebo (prior to protocol amendment 4.0) will be considered as being prior to study medication as well as concomitant for placebo.

7.1.4.4 Potential Hy's Law Criteria

Patients will be deemed as meeting potential Hy's law Criteria if their ALT or AST > 3x ULN and bilirubin > 2 x ULN at the same visit.

Further assessment to determine that no other reason can be found to explain the combination of increased aminotransferase and serum total bilirubin, such as viral hepatitis, alcohol abuse,

ischemia, pre-existing liver disease, or another drug capable of causing the observed injury will be conducted.

7.1.4.5 Duration of Hospitalisation

The duration of hospitalization (number of days) will be defined as:

(date of discharge – date of admission) + 1

7.2 Handling of missing data and outliers

7.2.1 Missing data analysis methods

Unless specified, data in summary tables will be presented using Observed Case (OC) data and therefore no missing data will be imputed.

For data listings, unless specified, all data will be presented as they have been recorded (e.g. missing and partial dates will not be replaced).

7.2.2 Handling of missing or incomplete data

7.2.2.1 Partial dates of last fracture

In order to calculate the time since last fracture, the following rules will be applied for partial dates:

- if the day of the month is missing it is imputed to be the 15th
- if both the day and month are missing, they are imputed to be June 30th
- missing years will be left as missing.

The above will be flagged and described as a footnote in the appropriate listings.

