7.1. Inclusion Criteria

Participants are eligible to be included in the study only if all of the following criteria apply:

Type of Participant and Disease Characteristics

1. Patients with a clinical diagnosis of OI Type I, III, or IV with a defect in COL1A1/COL1A2, as confirmed by genetic testing
2. Age \geq 18 years
3. One or more non-traumatic long-bone, rib, hand/feet and/or vertebral fracture(s) in the past 5 years

Sex

4. Male and female

NOTE: The reliability of sexual abstinence for female enrolment eligibility needs to be evaluated in relation to **the duration of the clinical study and the preferred and usual lifestyle of the participant**. Periodic abstinence (eg, calendar, ovulation, symptothermal, or postovulation methods) and withdrawal are not acceptable methods of contraception.

Male participants:

5. There are no contraception requirements for male participants with female partners who are woman of childbearing potential (WOCBP) (See [Appendix 5](#)).

Female participants:

6. A female participant is eligible to participate if she is not pregnant (see Appendix 5), not breastfeeding, and at least one of the following conditions applies:

- a. Not a WOCBP as defined in Appendix 5

OR

- b. A WOCBP who agrees to follow the contraceptive guidance in Appendix 5 during the treatment period and for at least 70 days after the last dose of setrusumab treatment.

Informed Consent

7. Capable of giving signed informed consent as described in [Appendix 3](#) which includes compliance with the requirements and restrictions listed in the informed consent form (ICF) and in this protocol.

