7.1.2 Definitions relative to demographic and other baseline characteristics

Age

Age at randomisation will be calculated as:

$$\text{Age (years)} = (\text{date of randomisation} - \text{date of birth} + 1) / 365.25$$

Weight, Height and BMI

Weight, recorded in pounds on the eCRF, will be converted in kilograms (1 pound = 0.45359 kg).

Height, recorded in inches on the eCRF, will be converted in centimetres (1 inch = 2.54 cm) (International System of Units).

Body mass index (BMI) will be calculated in kg/m^2 as: $\text{weight (kg)} / (\text{height (m)})^2$.

Temperature

Temperature, recorded in Fahrenheit degrees on the eCRF, will be converted in Celsius degrees:

$$\text{Celsius degrees} = (\text{Fahrenheit degrees} - 32) \times (5/9)$$

Time since last Fracture

Time since last Fracture in months will be calculated as:

$$(\text{Date of first dose of study medication} - \text{date of last fracture} + 1) / 30.4375$$

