8.4.2 Fracture/OI history

Fracture/ OI history including the number patients experiencing any fracture within the last 2 years (5 years from protocol amendment 4.0), time since last fracture (months), description of fracture (location), fracture anatomical location, percentage compression (vertebral only), evidence of interval healing, fracture history patient reported (Y/N), OI Type and COL1A1/COL1A2 testing (Y/N) will be summarised by treatment group and overall using the safety population.

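### The imputation rule for partial last-fracture dates has no upper limit at first dose, so the descriptive variable time since last fracture can come out zero or negative

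*SAP*

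**What the plan says.** SAP 7.2.2.1 limits its own scope: "In order to calculate the time since last fracture, the following rules will be applied for partial dates". Three rules follow. For a missing day, "if the day of the month is missing it is imputed to be the 15th". For a missing day and month, "if both the day and month are missing, they are imputed to be June 30th". Finally, "missing years will be left as missing". The only other instruction there is to flag and footnote imputed dates in the listings.

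The derived variable is defined in SAP 7.1.2: "Time since last Fracture in months will be calculated as" the first-dose date minus the last-fracture date, plus 1, divided by 30.4375. No minimum is set.

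SAP 8.4.2 lists it for summary by treatment group and overall on the Safety population: "time since last fracture (months), description of fracture (location), fracture anatomical location". Under SAP 8.1.3, continuous variables are reported with mean, SD, minimum, median and maximum.

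Protocol 7.1 requires "One or more non-traumatic long-bone, rib, hand/feet and/or vertebral fracture(s) in the past 5 years", with no minimum interval before first dose.

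**The concern.** The variable describes history before treatment, so a value below zero is impossible. The rule assigns the middle of the recorded month or year without asking whether the participant had already been dosed by then. If the fracture and first dose fall in the same month or year, the filled-in date can land after dosing. The eligibility window allows this, because a fracture shortly before entry qualifies.

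Elsewhere the SAP does tie partial dates to first dose: for medications and procedures in 7.2.2.3, and for adverse events in 7.2.2.4. The fracture rule has no such link.

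What is at stake is the baseline table in the study report. The records affected belong to participants whose last fracture was recent. An impossible value would appear as the arm's minimum and pull its mean down.

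**Working it through.** **Inputs.** The imputation rule is from SAP 7.2.2.1 and the formula from SAP 7.1.2. The SAP gives no figure on this point to reproduce. The calendar dates below are illustrative, because the documents contain no patient dates.

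**Formula.** Months = (first dose - last fracture + 1) / 30.4375, with dates counted in days.

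**Year-only record.** Fracture recorded as 2018, first dose 20 February 2018.
- The imputed date, 30 June 2018, is 130 days after dosing: (-130 + 1) / 30.4375 = -4.24 months.
- The fracture must really have fallen between 1 January and 19 February. The true value is therefore between 2 / 30.4375 = 0.07 and 51 / 30.4375 = 1.68 months.

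**Extreme year-only record.** First dose 2 January 2018: (-179 + 1) / 30.4375 = -178 / 30.4375 = -5.85 months. In a leap year it is -179 / 30.4375 = -5.88.

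**Month-and-year record.** Fracture recorded as February 2018, first dose 5 February 2018.
- The imputed date is 15 February: (-10 + 1) / 30.4375 = -0.30 months.
- The true value is between 2 / 30.4375 = 0.07 and 5 / 30.4375 = 0.16 months.

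**When it happens.** Because of the +1, an imputed date one day after first dose gives exactly zero, and two or more days after gives a negative value.
- Same year, year only: negative for first doses from 1 January to 28 June, 179 of 365 calendar days (49%).
- Same month, day missing: negative for first doses on days 1 to 13, 12 × 13 = 156 of 365 calendar days (43%).

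**Share of year-only records.** Assume first doses are spread evenly over a 365-day year and fractures evenly over a window before dosing. 30 June is day 181, so a dose on day d gives a value of zero or less when d is at most 180. A dose on day d has d - 1 earlier days in the same year.
- Among same-year records: (180 × 179 / 2) / (365 × 364 / 2) = 16,110 / 66,430 = 24%. This is below 49% because early dosing leaves fewer same-year days on which a fracture could have occurred.
- Among all year-only records: 16,110 / (365 × 365) = 12% for a 1-year window, 6% for 2 years and 2.4% for 5 years. SAP 8.4.2 names the 2- and 5-year windows; the 1-year window is an assumption.

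These are shares of year-only records, not of participants.

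**Effect on a summary.** With 25 participants in an arm (the planned size), one record like the first example lowers the arm mean by between (4.24 + 0.07) / 25 = 0.17 and (4.24 + 1.68) / 25 = 0.24 months.

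**After a cap at the day before first dose.** The 20 February and 5 February examples both become (1 + 1) / 30.4375 = +0.07 months.

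**The case against.** The best defence is that nothing depends on this variable. SAP 8.4 rules out formal comparison of baseline characteristics between regimens. The ANCOVA in SAP 8.5.1 uses treatment, stratum and the endpoint's own baseline. On-study time to first fracture (SAP 7.1.3.3) runs from first active dose to the date of diagnosis. Imputed dates are flagged in listings, a negative minimum would be seen in the table, and the median would barely move. The trigger also needs a partial date in the same year or month as dosing, and recent fractures may well be recorded in full.

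All of this stands as a limit on importance. It does not make the rule right. The flag covers listings, not the summary table. Seeing a negative minimum does not correct it, and a programmer who corrected it would be departing from the written rule, which SAP section 1 says must be described and justified in the study report.

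A reader might infer that the arms are compared on a key marker of fracture risk and that the comparison is biased. The documents do not support this: they plan no such comparison, do not call the variable a key risk marker, and stratify on OI type. Nor is eligibility affected, since the imputation is confined to this one derived variable.

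**Conclusion.** The rule as written gives wrong values for dates that the eligibility criteria allow. SAP 7.2.2.1 sets no upper limit, SAP 7.1.2 sets no floor, and neither document supplies one elsewhere. The result can be zero or negative, down to about -5.9 months for a year-only record, and by a fraction of a month when only the day is missing.

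The consequence is confined to the mean, minimum and related statistics in one baseline summary. No efficacy, dose-response or safety conclusion changes. The percentages rest on assumed even spreads of dosing and fracture dates. Without the number of partial dates, they cannot be turned into a count of participants. This is a minor correction, worth making because it is nearly free.

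**What to change.** Add one sentence to SAP 7.2.2.1: the imputed date is the earlier of the rule's date and the day before first dose of study medication. Use that reference date because SAP 7.1.2 does. First active dose, used for study day in SAP 7.1.1, may differ for participants who started on placebo. The cap removes impossible values but puts every capped record at 0.07 months, the low end of its possible range.

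An alternative uses more of the information. Whenever the dates consistent with the partial record include first dose, cut that range off at the day before first dose and take its midpoint. In the 20 February example the range is day 1 to day 50 and the midpoint is day 25.5, giving (51 - 25.5 + 1) / 30.4375 = 0.87 months.

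This must apply to all such records, not only those whose imputed date falls on or after first dose. Otherwise a year-only record dosed on 30 June would give (181 - 90.5 + 1) / 30.4375 = 3.0 months, and one dosed on 1 July would give 2 / 30.4375 = 0.07, a jump of about 3 months for one day's difference.

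Either version costs one sentence and about one line of code, and touches no other analysis.
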